3.2.2. Phase 1b

This is an open-label, multi-center, single-arm, Phase 1b study with 2 cohorts.

GS-1423 + mFOLFOX6: Cohort 1 (gastric cancer)

Cohort 1 will assess safety and tolerability and define the DLT and MTD or RP2D of GS-1423 in combination with a chemotherapy regimen (mFOLFOX6) in subjects with advanced (unresectable, recurrent or metastatic) gastric or gastroesophageal junction adenocarcinoma who have not previously received systemic therapy for advanced disease. GS-1423 and mFOLFOX6 will be administered starting on Day 1 of each 2-week cycle (Q2W). GS-1423 will be administered for up to 2 years and mFOLFOX6 will be administered for up to 12 cycles with option to continue leucovorin and 5-FU Q2W at investigator's discretion until the subject meets study treatment discontinuation criteria or for up to 2 years.

A standard 3+3 dose escalation design will be used to determine the DLT and MTD or RP2D of GS-1423 in combination with mFOLFOX6. A Safety Review Team (SRT) will assess safety and decide on dose escalation.

After the MTD or RP2D of GS-1423 in combination with mFOLFOX6 has been determined, the cohort will be expanded by adding approximately 70 subjects to explore the potential efficacy.

One futility interim analysis will be performed after approximately 50% of subjects have been enrolled and are able to complete study treatment for at least 6 months post safety run-in.

GS-1423 Monotherapy: Cohort 2 (Paired Biopsy)

Cohort 2 will assess safety and tolerability of GS-1423 monotherapy in multiple tumor types. GS-1423 will be administered on Day 1 of each cycle until the subject meets study treatment discontinuation criteria or for up to 1 year.

Cohort 2 will enroll subjects until 15 evaluable paired tumor biopsies (baseline and any on-treatment) have been collected, including a minimum of 5 biopsies from non-small-cell lung carcinoma (NSCLC) (non-squamous adenocarcinoma) and 5 colorectal cancer (CRC) or pancreatic cancer subjects.

3.2.3. Dose Escalation

3.2.3.1. Dose Escalation Procedure (Phase 1a Part A)

Subjects with advanced solid tumors who have failed or are intolerant to standard therapy or for whom no standard therapy exists will be sequentially enrolled at progressively higher dose levels to receive GS-1423.

The initial starting dose will be 0.3 mg/kg and the first cohort will be enrolled to confirm safety at this level. Subsequent doses of 1, 3, 10, 20, 30 and 45 mg/kg are planned.

[figure not shown]
Table 3-1. Phase 1a Part A GS-1423 Dose Levels and Cohorts

| Cohort | No. of Subjects | Escalation Type | Dose of GS-1423 (mg/kg) |
|-------------------|------------------------|------------------------|--------------------------------|
| 1 (starting dose) | 1 or 3-6 | Accelerated titration | 0.3 |
| 2 | 1 or 3-6 | Accelerated titration | 1 |
| 3 | 3-6 | 3+3 | 3 |
| 4 | 3-6 | 3+3 | 10 |
| 5 | 3-6 | 3+3 | 20 |
| 6 | 3-6 | 3+3 | 30 |
| 7 | 3-6 | 3+3 | 45 |

Note: An additional 6 subjects may be enrolled at a dose level at or below maximum tolerated dose to obtain additional safety, pharmacokinetics, and **CCI** information. Gilead may choose not to enroll any cohort if it is deemed unnecessary.

[figure not shown]
This part of study will utilize an accelerated titration design schema of dosing 1 subject each at the first 2 dose levels of 0.3 mg/kg and 1 mg/kg and with subsequent dosing conducted in a 3+3 dose escalation format ([Figure 3-1](#) and [Figure 3-2](#)). At the first 2 dose levels of 0.3 mg/kg and 1 mg/kg, if 2 or more drug-related adverse events (AEs) of Grade 2 or higher or at least 1 DLT are observed during the 28-day DLT observation period, the 3+3 escalation scheme will be used at that dose and subsequent doses. Each subject will stay on the dose level and schedule assigned at study entry.

Figure 3-1. Accelerated Dose Escalation Scheme

AE = adverse event; DLT = dose limiting toxicity

Figure 3-2. 3+3 Dose Escalation Scheme

DLT = dose limiting toxicity; MTD = maximum tolerated dose

Note: If MTD is attained at the first dose level, discussion with investigators and medical monitor to change dose or schedules in a protocol amendment

In each dosing cohort of more than 1 subject, the enrollment of the second subject will not proceed unless the first subject tolerated the therapy without DLT within the first 7 days following the first infusion. Thereafter, within each cohort in the dose escalation phase, consecutively enrolled subjects may initiate treatment \geq 24 hours after the prior enrolled subject initiated treatment. Each subject will be observed for a DLT observation period of 28 days from the initial dose of GS-1423, and 3 subjects must be able to receive and tolerate the first 2 doses of GS-1423 without DLTs during this observation period before the dose will be escalated and the next cohort begins enrollment.

If 1 of the first 3 evaluable subjects enrolled has a DLT within the first 28 days, then 3 additional subjects will be enrolled at the same dose level. If no DLTs are observed in the additional 3 subjects, dose escalation will occur. If a DLT occurs in \geq 2 subjects in the total cohort of 6 subjects, the MTD will be deemed to be exceeded, and the prior dose level will be evaluated to determine the MTD by increasing enrollment to 6 subjects. If the prior dose level was already deemed to be safe (ie, 0 or 1 DLT) and enrolled 6 subjects, then it will be defined as the MTD. If 2 or more subjects have DLTs within the first 28 days, dose de-escalation to a lower dose will occur. The MTD is the highest dose level with an incidence of DLTs of 0 or 1 out of 6 subjects during the first 28 days of study drug dosing. A minimum of 6 subjects need to be treated at a dose level before this dose level can be deemed as the MTD. A subject who is withdrawn from the study before the completion of the first 28 days for a reason other than a DLT will be replaced.

The SRT will review safety and relevant clinical data after all subjects in a cohort have reached the end of the DLT observation period of 28 days and make the dose escalation/stay/de-escalation decision. Source data verification is not required to be performed prior to dose escalation/SRT meetings. Alternative data quality control checks that are performed on data used to make dose escalation decisions are described in the SRT Charter.

Starting at Cohort 4 (10 mg/kg), if no DLT is observed during the 28-day DLT observation period in the first 3 subjects, 3 additional subjects may be enrolled at the respective dose level to obtain more safety, PK, and CCI data. If \geq 2 subjects have experienced DLTs in the last 3 (of 6) subjects, dose escalation will halt and up to 3 additional subjects will be enrolled at the preceding dose level (if there were only 3 subjects in that cohort) for DLT assessment. If 6 subjects were already evaluated, the preceding dose level will be considered as MTD.

If 0.3 mg/kg exceeds the MTD (ie, does not pass DLT evaluation), Gilead and investigators may consider alternative dose schedules based on available safety data. If needed, PK, and CCI data will be reviewed as well; this will require a protocol amendment. If an alternate schedule is tested and determined to be safe, re-escalation of GS-1423 will proceed according to the protocol amendment. Otherwise, dose escalation will continue until the MTD is reached or dosing with the maximum planned dose level (45 mg/kg) is completed without meeting the criteria for MTD.

The RP2D will be determined by Gilead based on all available relevant clinical data. The RP2D will not exceed the maximum tolerated dose evaluated in this study.

3.2.3.2. Dose Escalation/Safety Run-in for Phase 1b

Cohort 1 (gastric cancer)

Safety run-in: This part of study will utilize a 3+3 dose escalation scheme. The planned starting dose of GS-1423 will be targeted to achieve the exposure at -1 dose level of RP2D monotherapy (Q2W) determined from Phase 1a. GS-1423 will be administered in combination with mFOLFOX6. In each dose level, the enrollment of the second subject will not proceed unless the first subject tolerated the therapy without DLT within the first 7 days following the first infusion. Thereafter, within each dose level in the safety run-in phase, consecutively enrolled subjects may initiate treatment \geq 24 hours after the prior enrolled subject initiated treatment.

Each subject will be observed for a DLT observation period of 28 days from the initial dose of GS-1423, and 3 subjects must be able to receive and tolerate the first 2 doses of GS-1423 in combination with mFOLFOX6 without DLTs during this observation period before the dose will be escalated and the next dose level begins enrollment. The SRT will review safety and relevant clinical data after all subjects at a dose level have reached the end of the DLT observation period of 28 days and make the dose escalation/stay/de-escalation decision.

Table 3-2. Phase 1b Cohort 1 Safety Run-in GS-1423 Dose Levels

| Regimen | No. of Subjects | Escalation Type | Dose of GS-1423 (mg) |
|--------------------|------------------------|------------------------|-----------------------------|
| GS-1423 + mFOLFOX6 | 3-6 | 3+3 | -1 Dose 1 (Q2W) |
| GS-1423 + mFOLFOX6 | 3-6 | 3+3 | Dose 1 (Q2W) |

5 FU 5 fluorouracil; Q2W every 2 weeks; RP2D recommended Phase 2 dose
The mFOLFOX6 regimen consists of 1 LV 200 mg/m² or dl LV 400 mg/m² and oxaliplatin 85 mg/m² followed by bolus 5 FU 400 mg/m² and a 46 hour infusion of 5 FU 2400 mg/m². Administration of mFOLFOX6 will follow administration of GS 1423 on Day 1 of each cycle.

1 Dose 1: Will be targeted to achieve the exposure at -1 dose level of RP2D monotherapy (Q2W) determined based on cumulative data from Phase 1a.

Dose 1: Will be targeted to achieve the exposure at the dose level of RP2D monotherapy (Q2W) determined based on cumulative data from Phase 1a.

An additional 6 subjects may be enrolled at a dose level at or below MTD to obtain additional safety, PK, and CCI information.

3.2.3.3. Definition of Dose Limiting Toxicity

Toxicity will be graded according to National Cancer Institute Common Terminology Criteria for Adverse Events Version 5.0 (NCI CTCAE v5.0). A DLT is a toxicity observed in the first 28 days as defined below and considered possibly related to GS-1423.

A DLT may lead to permanent withdrawal of GS-1423 for the subject after discussion between the Investigator and Gilead.

Hematologic

- Grade 3 thrombocytopenia with clinically significant bleeding (ie, requires hospitalization, transfusion of blood products, or other urgent medical intervention)
- Grade ≥ 3 febrile neutropenia (absolute neutrophil count [ANC] $< 1.0 \times 10^9/L$ and fever $> 101^{\circ}\text{F}/38.3^{\circ}\text{C}$)
- Any Grade 4 hematologic laboratory abnormalities/AEs regardless of duration will be considered DLTs with the **exception** of

Grade 4 lymphopenia

Grade 4 neutropenia lasting ≤ 7 days that is not associated with fever (the use of growth factors is permitted)

Grade 4 anemia explained by underlying disease

Non-Hematologic

- Grade 4 non-hematologic (laboratory and non-laboratory) AEs will be considered DLT regardless of the duration
- Any \geq Grade 2 uveitis, blurred vision, eye pain, and/or reduction of visual acuity that does not respond to topical therapy and does not improve to Grade 1 severity within 2 weeks of the initiation of topical therapy OR requires systemic treatment will be considered as a DLT
- The following Grade 3 non-hematologic AEs **will be considered as DLTs**:

Any Grade 3 AE of unknown etiology consistent with an immune phenomenon that does not resolve to \leq Grade 1 or to baseline with immunosuppressive therapy within 3 weeks of its onset

Any Grade 3 central nervous system (CNS)-related AE of unknown etiology consistent with an immune phenomenon regardless of duration or reversibility

Alanine aminotransferase (ALT) or aspartate aminotransferase (AST) elevation $\geq 3 \times$ upper limit of normal (ULN), also showing elevation of serum total bilirubin of $> 2 \times$ ULN, without initial findings of cholestasis (elevated serum alkaline phosphatase)

- Any other non immune-related Grade 3 AE **except:**

Any Grade 3 endocrinopathy that is adequately controlled by hormonal replacement
Grade 3 AE of tumor flare (defined as local pain, irritation, or rash localized at sites of known or suspected tumor)
Transient (\leq 3 days) Grade 3 fatigue, local reactions, headache, nausea, emesis, or diarrhea that are controlled with medical management and/or resolves to Grade \leq 1
Transient (\leq 3 days) Grade 3 flu-like symptoms or fever, which are controlled with medical management
An event clearly associated with the underlying disease, PD, a concomitant medication, or comorbidity.

Dosing/procedures-related toxicities

- Inability to receive the first 2 doses of GS-1423 because of related toxicity, even if the toxicity does not meet DLT criteria defined above (regardless of dosing schedule)

Note: Exceptions include DLT exclusions mentioned above.

- Greater than a 2-week delay in starting the next cycle of therapy due to a treatment-related toxicity, even if the toxicity does not meet the DLT criteria determined above

Grade 5 event (ie, death)

3.2.3.4. Stopping Rules for Toxicity

The SRT will meet to review any cohort under evaluation as well as the safety of all cohorts. In cohorts with more than 1 subject, should $> 33\%$ subjects on any dose level have toxicities that meet DLT criteria after the DLT observation period of 28 days or in subjects not included in the DLT analysis, the occurrences will be thoroughly evaluated by the committee. Subjects not included in the DLT analysis set are those who discontinued during the DLT period for reasons other than DLT. The SRT will then make recommendations to initiate any changes in study conduct.

If there is a subject death within 30 days of initial study drug administration (Day 1) for reasons directly related to study treatment, enrollment in the study and/or treatment will be put on hold as appropriate. The SRT will then evaluate the cause of the event and recommend the appropriate change in study conduct to be communicated with health authorities. If the event is determined to be related to study treatment, then a study amendment and/or other corrective action plan will be established by the SRT in conjunction with health authorities.

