3.2.4. Safety Review Team

An SRT will be established to assess safety, make decisions on dose escalation, and define the DLT and MTD.

For any given cohort, Gilead may elect to hold dosing, select an intermediate dose, or stop study enrollment at any time based on review of the preliminary safety data.

Based on review of relevant safety data by the SRT, as specified in Section [3.2.3.1](#), and in discussion with the investigator, escalation to a higher dose will occur only in the absence of > 1 DLTs per dose level and/or meeting any prespecified stopping criteria.

The SRT will consist of at least 1 investigator and the Gilead medical monitor. Others may be invited to participate as members of the SRT if additional expertise is desired (ie, representatives from Pharmacovigilance and Epidemiology [PVE], Clinical Operations, Biostatistics, Clinical Pharmacology and Biomarker Sciences as applicable). The medical monitor serves as the chair of the SRT. An SRT Charter will be agreed by all SRT members prior to the first SRT meeting. The data reviewed at the SRT to make dose escalation decisions will be defined in the SRT Charter. The quality control checks performed on the data reviewed and used for making dose escalation decisions will be described in the SRT Charter.

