8.2. Planned Analyses

8.2.1. Interim Analysis

8.2.1.1. Dose Escalation Analysis

For the purpose of making the decision to escalate to the next dose level/cohort, interim analyses of relevant safety and PK (if available) data will be conducted by Gilead after all subjects in each cohort have completed dosing and the follow-up period as defined in Section 3.2.3. Safety assessments (ie, AEs, ECG, and laboratory results) will be displayed by dose level/cohort to facilitate the decision to dose escalate.

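### The related-death rule in Protocol 3.2.3.4 runs 30 days from the first dose, so one later related death has no event-specific trigger in the protocol text unless the >33% late-toxicity rule is met

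*Protocol*

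**What the plan says.** Protocol Section 3.2.3.4 contains two triggers.

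The first concerns death. Its condition is "If there is a subject death within 30 days of initial study drug administration (Day 1) for reasons directly related to study treatment". Three things follow. First, "enrollment in the study and/or treatment will be put on hold as appropriate". Second, "The SRT will then evaluate the cause of the event and recommend the appropriate change in study conduct to be communicated with health authorities". Third, if the SRT concludes that the death was related, a protocol amendment or another corrective plan, worked out with health authorities, becomes mandatory.

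The second concerns late toxicity. In cohorts of more than one subject, if over 33% of subjects on a dose level "have toxicities that meet DLT criteria after the DLT observation period of 28 days or in subjects not included in the DLT analysis", then "the occurrences will be thoroughly evaluated by the committee", and the SRT makes recommendations. No hold is named. Section 3.2.3.3 lists a Grade 5 event among the DLT criteria, so a related death after Day 28 counts towards this rule.

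Other provisions are general. Section 3.2.3.1 states: "The SRT will review safety and relevant clinical data after all subjects in a cohort have reached the end of the DLT observation period". Section 8.2.1.1 states: "interim analyses of relevant safety and PK (if available) data will be conducted by Gilead after all subjects in each cohort have completed dosing". Section 3.2.3.4 also has the SRT review the safety of all cohorts, without a stated schedule. Section 3.2.4 adds that "Gilead may elect to hold dosing, select an intermediate dose, or stop study enrollment at any time based on review of the preliminary safety data".

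On exposure, Section 3.4 allows up to one year of treatment in Part A, which is 26 cycles on the two-weekly schedule. Section 5.5.4 says that immune-related events may appear only after weeks of treatment and can occur until several months after dosing stops.

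**The concern.** The death rule is anchored to the first dose, while both the exposure and the toxicity expected of this class run well beyond Day 30. The explicit reference to Day 1 leaves no room to read the window as counted from the last dose.

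This is a first-in-human study (Section 1.2.3). A directly related death on Day 29 requires an SRT cause evaluation and a decision on a hold. The same death two weeks later, at a level with 6 or 12 subjects, requires neither by its own occurrence. Meanwhile subjects at dose levels already open may still be dosed or enrolled. A later related death is also outside the DLT definition, which is limited to the first 28 days, so it does not enter the count of DLTs on which Section 3.2.4 conditions escalation.

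**Working it through.** The plan gives no figure to reproduce here. The check sets the window against the dosing calendar, then asks when one late death would meet the back-up rule.

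**1. Doses inside the window.** Inputs: 14-day cycles and at most 26 cycles (3.4); window of 30 days from Day 1 (3.2.3.4). Dose k falls on day 1 + 14(k − 1).
- Doses 1, 2 and 3 fall on Days 1, 15 and 29; dose 4 falls on Day 43; dose 26 falls on 1 + 14 × 25 = Day 351.
- Inside the window: 3/26 = 11.5%. After it: 23/26 = 88.5%. Counting Day 1 as day 0 changes nothing, because the next dose is on Day 43.

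**2. Time inside the window, by how long a subject stays on treatment.** The period at issue is first dose to 30 days after the last dose.
- Last dose Day 29: 30/(29 + 30) = 30/59 = 51%.
- Last dose Day 71 (dose 6): 30/(71 + 30) = 30/101 = 30%.
- Last dose Day 351 (all 26): 30/(351 + 30) = 30/381 = 7.9%.

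These are shares of doses and time, not risks. Many subjects will stop early.

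**3. Does the >33% rule catch one late death?** Smallest number of affected subjects x with x/n above the threshold:

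| Subjects on level (n) | One event, 1/n | x if threshold is 0.33 | x if threshold is one third |
|---|---|---|---|
| 3 | 33.3% | 1 | 2 |
| 4 | 25.0% | 2 | 2 |
| 5 | 20.0% | 2 | 2 |
| 6 | 16.7% | 2 | 3 |
| 12 | 8.3% | 4 | 5 |

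Here n = 12 is a full level of 6 plus the optional 6 at or below the MTD (Table 3-1). One death meets the rule at n = 3 only if 33% is read literally, and it does not meet the rule from n = 4 upwards. One-subject cohorts, planned at 0.3 and 1 mg/kg, are outside the rule.

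**4. Does the pre-escalation review fill the gap?** That review is timed by cohort completion, not by an event. After the last cohort's own Day 28 review no escalation decision follows. For the last-enrolled subject of that cohort, 2 doses (Days 1 and 15) fall by Day 28, so up to 24/26 = 92% of planned doses come after it.

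**5. Do the remaining provisions supply a trigger?** The sponsor's power in 3.2.4 is optional. The discontinuation clause in 3.5 is a general risk-benefit judgment. Sections 7.3.2 and 7.4 deliver information but require no SRT cause review. SAP Section 7.1.6.3 only lists and summarizes late events that meet the DLT definition. None is tied to a single late related death.

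**The case against.** The strongest reply is that oversight does not stop on Day 30. The SRT must review the safety of all cohorts, each new dose level needs an SRT decision, the sponsor can hold dosing at any time, SAEs reach the sponsor within 24 hours, and SUSARs go to regulators and investigators. The hold is discretionary even for a Day 29 death. SRT detail is deferred to a Charter that was not available and may provide an event-driven meeting. All of this stands. It narrows the gap to an automatic cause evaluation and its consequences, but it does not supply the trigger. The sponsor wrote a specific rule for early related deaths although the same safeguards were in place.

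Two further objections also stand. Widening the window extends the mandatory amendment or corrective plan as well as the discretionary hold, so the change is not free of consequence. It is also a partial remedy, because deaths later than 30 days after the last dose remain outside it.

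A reader might infer more than the documents support:
- That a new, higher dose level could open after a late related death with no SRT review. Sections 3.2.3.1 and 3.2.4 rule that out.
- That the sponsor lacked authority to act, or would not hear of the death. Sections 3.2.4, 7.3.2 and 7.4 say otherwise.
- That the 88.5% or 92% figures measure risk. They describe a subject who receives every planned dose.
- That ongoing enrolment was exposed to the gap. SAP Section 1 says the study was terminated early at the completion of Part A and that Part B and Phase 1b will not be initiated. The documents do not say whether any such death occurred or whether any subject was still on treatment.

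**Conclusion.** The point holds as a missing trigger in the protocol text. Three consequences of a directly related death are limited to 30 days from the first dose, a window that covers 3 of 26 planned Part A doses. One later related death sets none of them in motion, and it reaches the >33% rule only at a small level: 1 of 3 on a literal reading, but not 1 of 6 or 1 of 12. Even then the result is evaluation and recommendations, with no hold named.

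This is a cheap improvement, not a failure of oversight. Confidence is high for the wording of the protocol only. Whether a working gap existed depends on the SRT Charter. Because the study ended at completion of Part A, the point concerns the protocol as written.

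**What to change.** In the death clause of Section 3.2.3.4, replace the 30-day window counted from Day 1 with: from first dose through 30 days after the last dose. Leave the rest of the paragraph unchanged, including the requirement of direct relatedness, the discretionary hold, the cause evaluation and the amendment or corrective plan. Mirror the change in the SRT Charter.

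No new data are needed, because Section 7.3.2 already requires SAEs and deaths to be reported to 30 days after the last dose. The same cut-off is used for adverse events (7.3.1), safety summaries (8.7) and the death table in SAP Section 7.1.6.2. Deaths after that point stay under 7.3.2 reporting and the general safeguards.

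The cost is possible extra SRT reviews or short pauses and, for each death confirmed as related, the amendment or corrective plan that the paragraph already mandates. As an illustration, assume a per-subject risk of 0.5% to 2% for a related death after Day 30 and within 30 days of the last dose; this range is an assumption, not a figure in the documents. With up to 53 Part A subjects:
- Expected triggers: 53 × 0.005 = 0.27 to 53 × 0.02 = 1.06.
- Chance of at least one: 1 − 0.995^53 = 23% to 1 − 0.98^53 = 66%.

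Under that assumption this is an upper bound on extra reviews, since some of these deaths would already meet the >33% rule.
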